In the event that study discontinuation and withdrawal of a subject is necessary, the investigator should make every attempt to complete all protocol safety assessments and visits. Unless consent has been withdrawn, any subject is considered to be in the treatment phase of the study until the completion of the study, and such subjects should continue to be followed and will be expected to complete all safety assessments and visits.

11.8. Early Exit Criteria, Cohorts 2 and 3

Patients may also exit the study sooner than their exit visit if all of the following are true:

- They have received rescue therapy
- Their IOP in the study eye is well controlled
- No implant remnants are visible by gonioscopy on two consecutive visits
- No treatment related adverse events are present that require continued monitoring.

Communication

12. PROCEDURE SCHEDULE BY STUDY VISIT, COHORT 2

12.1. Visit 1/-49 to -29 days/Screening Evaluation, Cohort 2

At Visit 1, patients will be screened, and if eligible, enrolled into the study. Before any study specific assessments are performed, written informed consent will be obtained from each patient. Screening procedures can be conducted over several visits but should be completed within a 7 day period. During the visit, the procedures described below will be performed.

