2. PROTOCOL SUMMARY

ENV515-01 is a multicenter, open-label, prospective, active-comparator-controlled Phase 2a study of ENV515 (travoprost) Intracameral Implant comprising three stages:

- The completed Cohort 1 was a 28-day study focused on evaluation of the initial safety, efficacy, and pharmacokinetic properties of ENV515 conducted in glaucoma patients scheduled for cataract removal during which the ENV515 implant is removed during the cataract procedure 28 days after implantation. This cohort was covered in a separate SAP and no further mention of this cohort will be made in this SAP.
- Cohort 2 is a 12-month study with a 6-month optional Extension 1 followed by an additional 3-month optional Extension 2 (for a total of up to 21 months) that is focused on evaluation of the long-term safety and efficacy in glaucoma patients during which the two ENV515-3 implants are followed through their biodissolution while the duration of intraocular pressure (IOP)-lowering efficacy is assessed.
- Cohort 3 is a 12-month study with a 6-month optional Extension 1 followed by an additional 6-month optional Extension 2 (for a total of up to 24 months) that is focused on evaluation of the long-term safety in glaucoma patients during which one or two ENV515-3-2 implants per study eye are followed through their biodissolution.

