2.2 Overall Study Design and Plan

Cohorts 2 (5 patients) and 3 (15 patients) are 12-month, prospective, open-label, active-comparator-controlled, multicenter, dose-escalating cohorts of this Phase 2a trial. Cohort 2 had a 6-month optional Extension 1 followed by an additional 3-month optional Extension 2 (for up to a total of 21 months), increasing the total study duration to approximately 23 months. Cohort 3 has a 6-month optional Extension 1 followed by an additional 6-month optional Extension 2 (for a total of 24 months), increasing the total study duration to approximately 26 months. Cohorts 2 and 3 were designed to assess the long-term safety, tolerability, and systemic exposure to travoprost after a single low dose (ENV515-3) in Cohort 2, and single low or high doses (ENV515-3-2) in Cohort 3 in

patients with bilateral open-angle glaucoma or ocular hypertension (see Inclusion Criteria in Section 11.1 of the protocol). For the purposes of the Cohorts 2 and 3, patients are eligible if in the opinion of the investigator they have an IOP in both eyes that is considered to be adequately controlled at the screening visit, can be safely withdrawn from IOP medications in both eyes during the washout period, and are not considered to be at significant risk for disease progression throughout the trial. The dose levels of travoprost in Cohorts 2 and 3 of this study are achieved by administration of a single, unilateral intracameral injection of each formulation with 28.2 µg travoprost/eye in Cohort 2; and 26.1 µg and 52.2 µg travoprost/eye in Cohort 3. These dose levels will be achieved via two implants per eye for low dose of ENV515-3 in Cohort 2, and one and two implants per eye for the low and high doses of ENV515-3-2, respectively, in Cohort 3. The study eye is prospectively defined as the eye with higher IOP or the left eye if IOP values are equal in both eyes on Dosing Visit (Day 1). All non-study eyes will receive open-label timolol maleate 0.5% ophthalmic solution administered twice a day (Figure 1 and Figure 2).

Figure 1: ENV515 Treatment, Cohort 2

Treatments for the Study Eye vs. Non-Study, Fellow Eye

[figure not shown]
[figure not shown]

Figure 2: ENV515 Treatment, Cohort 3

Treatments for the Study Eye vs. Non-Study, Fellow Eye

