3. GENERAL ANALYSIS AND REPORTING CONVENTIONS

The following is a list of general analysis and reporting conventions to be applied for this study.

- Categorical variables will be summarized using counts (n) and percentages (%) and will be presented in the form "n (xx.x)". To ensure completeness, summaries for categorical and discrete variables will include all categories, even if no subjects had a response in a particular category.
- Continuous variables will be summarized using mean, standard deviation (SD), minimum, maximum, median, and number of subjects. The mean and median will be reported to one more level of precision than the original observations, and the SD will be reported to 2 more levels of precision than the original observations. The minimum and maximum will be the same precision as the original data.
- All analyses will be performed using SAS® System version 9.4 or higher.
- Dates will be displayed as ddmmmyyyy (e.g., 24Jan2005).

Patient-level analyses will be presented with the following columns:

Cohort 2	Low Dose Cohort 3	High Dose Cohort 3
2 implants ENV515-3	1 implant ENV515-3-2	2 implants ENV515-3-2
(28.2 µg travoprost)	(26.1 μg travoprost)	(52.2 µg travoprost)

Eye-level analyses will be presented with the following columns:

Cohort 2		Low Dose Cohort 3		High Dose Cohort 3	
2 implants ENV515-3 (28.2 µg travoprost)		1 implant ENV515-3-2 (26.1 μg travoprost)		2 implants ENV515-3-2 (52.2 µg travoprost)	
ENV515-3 SE	Timolol maleate 0.5% NSE	ENV515-3 SE	Timolol maleate 0.5% NSE	ENV515-3 SE	Timolol maleate 0.5% NSE

Note: SE=study eye, NSE=non-study eye

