9. SAFETY EVALUATION

9.1 Overview of Safety Analysis Methods

Adverse events, clinical laboratory results, vital signs, and physical exam findings will be tabulated at the subject level. All other safety measurements will be made at the eye level. Unless otherwise noted, baseline will be defined as the last measurement prior to receiving the implant.

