9.3 Adverse Events

Adverse events will be coded using the Medical Dictionary for Regulatory Activities (MedDRA) version 18.0 and categorized by system organ class using preferred terms. Events will be tabulated overall and by ocular/non-ocular status. Treatment related adverse events and severe adverse event will also be summarized. Serious adverse events will be summarized.

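### The Cohorts 2/3 adverse-event tables show whole-study percentages side by side without a common window or any report of time observed (planned maximum 21 v 24 months)

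*SAP*

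**What the plan says.** All SAP references are to the January 2019 SAP for Cohorts 2 and 3 unless stated.

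- **Content of the AE tables.** Section 9.3: "Events will be tabulated overall and by ocular/non-ocular status". Related, severe and serious events are also summarised. The six tables are 14.3.1.1 to 14.3.1.6 in Section 11.
- **Unit and statistic.** Section 9.1: "Adverse events, clinical laboratory results, vital signs, and physical exam findings will be tabulated at the subject level". Section 3: "Categorical variables will be summarized using counts (n) and percentages". Section 9.3 does not name a statistic itself, so patient n (%) is read from these two conventions.
- **Layout.** Section 3: "Patient-level analyses will be presented with the following columns", followed by Cohort 2, Cohort 3 low dose and Cohort 3 high dose.
- **Planned follow-up.** Section 2.2: "Cohort 2 had a 6-month optional Extension 1 followed by an additional 3-month optional Extension 2 (for up to a total of 21 months" and, for the other cohort, "Cohort 3 has a 6-month optional Extension 1 followed by an additional 6-month optional Extension 2 (for a total of 24 months".
- **Early exit.** Protocol Section 11.8: "Patients may also exit the study sooner than their exit visit if all of the following are true". The four conditions are prior rescue, controlled IOP in the study eye, no visible implant remnants at two consecutive visits, and no treatment-related AE needing continued monitoring.
- **Nearest thing to follow-up time.** Section 9.2 and Table 14.3.5.1 count days from insertion to implant dissolution or removal. Section 5.1 and Table 14.1.1 count completers, discontinuations and reasons.

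**The concern.** Protocol Section 17.1 has AEs monitored throughout the study, so a patient watched longer has more chance of being counted. If columns differ in time observed, their percentages can differ with no difference in safety. No planned output separates the two explanations: Table 14.3.5.1 measures how long the implant was present, and Table 14.1.1 measures who finished.

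Three features make this worth attention.

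1. Long-term safety and tolerability in a dose-escalating design is the only objective in SAP Section 2.1.
2. SAP Section 10 moves corneal thickness, endothelial cell, slit-lamp, fundus, visual-field and pupil summaries to listings. Much of the ocular safety evidence that is still summarised therefore sits in the AE tables.
3. Time observed may be related to outcome. A patient with a related AE needing monitoring cannot use the early-exit route, while one without it can.

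The events most exposed are those that can accrue slowly. Protocol Table 13 (Cohort 2 interim) lists endothelial cell loss in 2 of 5 patients, attributed to the implant, with one case ongoing.

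**Working it through.** **The plan's own figure.** The only numerical safety justification for these cohorts is in Protocol Section 18.2, Tables 19 and 20: the probability of seeing no toxicity, (1−p)^n. For n=5 and p=0.30, 0.7^5 = 0.168, which matches the stated 0.17. The other numeric entries also reproduce. The calculation has no time element, so it neither supports nor answers the concern.

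**Inputs.** Follow-up milestones of 12, 18, 21 and 24 months (SAP Section 2.2). Column sizes of 5 (SAP Section 2.6), 6 and 9 (Protocol Section 10.4). The documents give no hazard and no actual extension uptake. Both are therefore assumptions, shown over a range.

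**Step 1: constant hazard, identical in every column.** With p the 12-month risk, the expected crude proportion at T months is P(T) = 1 − (1−p)^(T/12). For p = 20%:

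- 12 months: 20.0%
- 18 months: 1 − 0.8^1.5 = 28.4%
- 21 months: 1 − 0.8^1.75 = 32.3%
- 24 months: 1 − 0.8^2 = 36.0%

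Ratio of crude percentages when true risk is equal:

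| 12-month risk | 24 v 21 months | 24 v 18 months | 24 v 12 months |
|---|---|---|---|
| 5% | 1.14 | 1.32 | 1.95 |
| 10% | 1.13 | 1.30 | 1.90 |
| 20% | 1.11 | 1.27 | 1.80 |
| 50% | 1.07 | 1.16 | 1.50 |

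The last column equals 2 − p.

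**Step 2: partial uptake.** Suppose Cohort 3 all reach 24 months, a share f of Cohort 2 reaches 21 months and the rest stop at 12. With p = 10%, the ratio is P(24) / [f·P(21) + (1−f)·P(12)]:

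- f = 0: 1.90
- f = 40% (2 of 5 patients): 1.49
- f = 80% (4 of 5): 1.23
- f = 100%: 1.13

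**Step 3: front-loaded events.** Take a 40% risk at the procedure plus a 10% late risk per 12 months. At 12 months the proportion is 1 − 0.6×0.9 = 46.0%. At 24 months it is 1 − 0.6×0.81 = 51.4%. The ratio is 1.12 even at the extreme contrast.

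**Step 4: chance.** One patient is 1/5 = 20, 1/6 = 17 or 1/9 = 11 percentage points. At p = 20%, the shift between 21 and 24 months is 36.0 − 32.3 = 3.7 points, less than one patient in any column.

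**Step 5: candidate remedies.** Cutting at Month 12 gives p in every column, a ratio of 1.00, provided nobody left earlier. An overall rate per patient-year also gives 1.00 under a constant hazard (0.105 in every column at p = 10%), but not for front-loaded events. With 0.4 injection-related events per patient and none later, the rate is 0.4/1 = 0.4 per patient-year over 12 months and 0.4/2 = 0.2 over 24. That is a two-fold artefact in the opposite direction.

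**The case against.** The strongest reply is that the design difference is small, the data are front-loaded and the tables are only descriptive.

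- **Small by design.** The two Cohort 3 columns share one visit schedule and the same extensions, so no follow-up difference is planned between low and high dose. The Protocol's Cohort 3 Extension 1 synopsis describes 18 months' duration for 15 patients, which is everyone dosed. Across cohorts the planned maxima are 21 and 24 months. This stands, with two limits: the same synopsis calls the extension an option, and uptake of Extension 2 by dose is not documented.
- **Front-loaded.** Protocol Section 1.5.2 describes the Cohort 2 ocular events as generally related to the injection. In Protocol Table 10 (Cohort 1), the number of patients with an ocular AE in Days 1-7 equals the number with any ocular AE in all four ENV515 groups (4, 7, 2 and 2). This stands for procedural events. Cohort 1 implants were removed at Day 28, however, so those data say little about late events. Endothelial cell loss and corneal edema were attributed to the implant in Cohort 2.
- **Descriptive, abbreviated report.** No AE test is described, the IND is being withdrawn (SAP Section 1), and all 20 patients can be inspected in the listings. This argues for a light remedy. It does not supply follow-up time in any table.

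A reader might infer that the columns themselves run from under 12 to 24 months, so that equal risks will look nearly two-fold different and the tables cannot be interpreted. The documents do not support that. Follow-up under 12 months is possible for an individual who meets all four exit conditions; it is not a property of a column. Nothing suggests that one whole column left at Month 12 while another stayed to Month 24.

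**Conclusion.** The point holds in moderate form. The SAP shows crude whole-study AE percentages in adjacent columns with unequal and partly optional follow-up, and no table reports time observed.

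At the planned maxima the spurious ratio is about 1.1, and at 18 v 24 months about 1.3. It reaches 1.8 to 1.95 only in the extreme split, for 12-month risks of 20% down to 5%. All these figures assume a constant hazard common to the columns, which the documents neither state nor contradict for late events. Early procedure-related events are hardly distorted. With 5, 6 and 9 patients, chance is at least as large an obstacle to reading across columns as the planned follow-up difference.

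Actual follow-up is not in the documents, so the true distortion cannot be fixed within that range. A reader of the planned tables could not place it either, which is the reason to act. It matters most for implant-attributed events that can accrue over time. This is a cheap improvement and does not invalidate the safety analysis.

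**What to change.** 1. In Tables 14.3.1.1 to 14.3.1.6, keep the whole-study n (%) and add n (%) of patients with onset up to the Month 12 visit. Footnote any patient who left before Month 12, with time observed and reason.
2. In Table 14.1.1, add follow-up time per column (median and range, first dose to last visit) and the number of patients reaching Months 12, 18, and 21 (Cohort 2) or 24 (Cohort 3).
3. Do not add an overall events-per-patient-year rate, because injection-related events make it fall as follow-up lengthens (Step 5). If a rate is wanted, limit it to late-onset events such as endothelial cell loss.

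The cost is a few extra rows in an abbreviated report, computed from dosing, onset and exit dates. No new data collection is needed.

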9.4 Clinical Laboratory Evaluation

Continuous clinical laboratory values will be summarized using descriptive statistics for reported and change from baseline values. Baseline will be the last measurement prior to implantation. Categorical clinical laboratory values will display the frequencies of patients with abnormal and normal results.

9.5 Vital Signs, Physical Findings, and Other Observations Related to Safety

9.5.1 Vital Signs

Vital sign assessments include measurements of heart rate, blood pressure, and respiration rate. Vital signs will be summarized using descriptive statistics by study visit and treatment group. All vital sign data will be presented in subject listings.

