- 22. Are an employee of the clinical site that is directly involved in the management, administration, or support of this study or are an immediate family member of the same
- 23. Patients who, per investigator's judgment, are not good clinical trial candidates due to personal (e.g., perceived willingness or ability to comply with protocol, significant traveling distance to medical center) and/or medical (e.g., mental illness, other non-ocular medical conditions, or laboratory abnormalities that might negatively impact trial participation or outcome) conditions that would likely impede the patient's successful study completion or planned analyses.

Response Measures:

Safety Measures: Assessed by evaluating changes from baseline in the following:

- Specular microscopy (non-contact)
- Slit-lamp biomicroscopy
- Corneal staining
- Dilated fundus examination
- Gonioscopy exam
- Anterior chamber OCT exam
- Pupil measurement
- Pachymetry (contact)

- BCVA
- Visual Field
- Body system assessment
- Vital signs
- Non fasting clinical laboratory tests (chemistry and hematology)
- Urine pregnancy tests for females of childbearing potential
- AEs

Pharmacokinetic Measures:

• Systemic exposure to travoprost via analysis of travoprost acid in plasma

31

Table 5: Time and Events Schedule, Cohort 3¹¹

Note: V16/Month 12 Time and Events Schedule should only be used if patients are not continuing into the Cohort 3 Study Extension 1 and plan to exit the study at V16/Month 12. If the patient is continuing into the Cohort 3 Study Extension 1, V16/Month 12 should follow the Time and Events Schedule in the Cohort 3 Study Extension 1 Synopsis, Table 6.

Procedure	Screening V1 Day -56 to -42	Baseline V2 Day -7 to -1	Dosing V3 Day 1	Treatment V4, 5,5a,6 Day 2,14,28, 42 +/- 3 days	Treatment V7 Day 84 +/- 7 days	Treatment V8,9 Month 4,5 +/- 7 days	Treatment V10 Month 6 +/- 7 days	Treatment V11 Month 7 +/- 7 days	Treatment V12 Month 8 +/- 7 days	Treatment V13 Month 9 +/- 7 days	Treatment V14 Month 10 +/- 7 days	Treatment V15 Month 11 +/- 7 days	Exit/Early Exit V16 Month 12 +/- 7 days
Informed consent review	X		I.										
Demo-graphics/ medical & ocular history	X												
Eligibility Criteria Confirmation Prior to Dosing	X	X	X										
Concomitant medication query	X	X	X	X	X	X	X	X	X	X	X	X	X
Adverse events query	X	X	X	X	X	X	X	X	X	X	X	X	X
BCVA – (ETDRS) With manifest refraction	X	X	X	X	X	X	X	X	X	X	X	X	X
Pupil measurement	X	X		X^1	X	X	X	X	X				

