Diurnal IOP curves will be measured at select study visits with the exception of the abbreviated visits at the Screening Visit (Days -49 to -42 for Cohort 2 and Days -56 to -42 for Cohort 3) Dosing Visit 3 (Day 1), Treatment Visit 4 (Day 2), and Treatment Visit 5a (Day 28), and selected visits depending on the Cohort and Extension(s).

Throughout the study, patients will undergo multiple safety assessments. A schedule of assessments is outlined in the sections below and in Table 1, Table 2, Table 3, Table 4, Table 5, Table 6, and Table 7.

10.1. Safety Evaluations, Cohorts 2 and 3

10.1.1. Review of Safety Data by Medical Monitor, Cohorts 2 and 3

A review of unmasked ocular safety data from each patient will be performed on an ongoing basis by a medical monitor. All ocular safety data for each patient will be provided to the medical monitor as it is generated throughout the trial. A patient may be discontinued at any time during the study at the discretion of the medical monitor for reasons referenced in, but not limited to Section 15.2.1. In addition, a meeting with the Envisia project team may be requested by the medical monitor at any time during the study to conduct a full evaluation of safety, which may result in a recommendation to terminate the study.

10.2. Safety Endpoints, Cohorts 2 and 3

The safety endpoints of the Cohorts 2 and 3 phases of this study are:

- Incidence of AEs;
- Changes in ophthalmic examination parameters (slit-lamp biomicroscopy, corneal staining, dilated funduscopic exam, anterior segment photos, pupil measurement,

using program 24-2);

Confidential

ocular symptom questionnaire, and VF as measured by the Humphrey Field Analyzer

- Changes in endothelial cell count and endothelial cell morphology using specular microscopy;
- Changes in corneal thickness as measured using pachymetry;
- Changes in IOP, including diurnal curve, as measured using a Goldmann applanation tonometer;
- Changes in BCVA with manifest refraction using the ETDRS chart;
- Changes in body systems assessment, vital signs, and laboratory parameters;
- Rate of discontinuation from the study; and
- Drug levels (travoprost free acid) in plasma.

10.3. Endpoints, Cohorts 2 and 3

10.3.1. Trial Treatments, Cohorts 2 and 3

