Envisia Therapeutics Protocol No. ENV515-01		CONFIDENTIAL		Statistical Analysis Plan 23SEP2015
		Study Eye		
AE_TAF	33	Number and Percentage of Subjects with Adverse Events by Treatment Group, System Organ Class, Preferred Term and Severity for Study Days 19-25 – Study Eye	Safety	
AE_TAF2	34	Number and Percentage of Subjects with Adverse Events by Treatment Group, System Organ Class, Preferred Term and Severity for Study Days 19-25 – Non- Study Eye	Safety	
AE_TAG	35	Number and Percentage of Subjects with Treatment- Related Adverse Events by Treatment Group, System Organ Class, Preferred Term and Relationship to Study Treatment – Study Eye	Safety	
AE_TAG2	36	Number and Percentage of Subjects with Treatment- Related Adverse Events by Treatment Group, System Organ Class, Preferred Term and Relationship to Study Treatment – Non-Study Eye	Safety	
AE_TAG3	37	Number and Percentage of Subjects with Treatment- Related Adverse Events by Treatment Group, System Organ Class, Preferred Term and Relationship to Study Treatment – Non- Ophthalmic Adverse Events	Safety	
AE_TAH	38	Number and Percentage of Subjects with Treatment- Related Adverse Events by Treatment Group System Organ Class, Preferred Term and Relationship to Study Treatment for Study Days 1-	Safety	

Invisia Therapeutio Protocol No. ENV5		CONFIDENTIAL		Statistical Analysis Plan 23SEP2015
		7 – Study Eye		
AE_TAH2	39	Number and Percentage of Subjects with Treatment- Related Adverse Events by Treatment Group System Organ Class, Preferred Term and Relationship to Study Treatment for Study Days 1- 7 – Non-Study Eye	Safety	
AE_TAI	40	Number and Percentage of Subjects with Treatment- Related Adverse Events by Treatment Group System Organ Class, Preferred Term and Relationship to Study Treatment for Study Days 19-25 – Study Eye	Safety	
AE_TAI2	41	Number and Percentage of Subjects with Treatment- Related Adverse Events by Treatment Group System Organ Class, Preferred Term and Relationship to Study Treatment for Study Days 19-25 – Non-Study Eye	Safety	
VS_TAA	42	Mean and Mean Change from Baseline in Vital Sign Values by Treatment Group and Visit	Safety	
LB_TAA	43	Mean and Mean Change from Baseline in Blood Chemistry Values by Treatment Group and Visit	Safety	
LB_TAB	44	Mean and Mean Change from Baseline in Hematology Values by Treatment Group and Visit	Safety	
LB_TAC	45	Mean and Mean Change from Baseline in Continuous Urinalysis Values by Treatment Group and Visit	Safety	
LB_TAD	46	Summary of Categorical	Safety	

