9.5.3 Visual Acuity (VA)

Visual acuity will be measured using the Early Treatment Diabetic Retinopathy Study (ETDRS) chart according to the manufacturer's specifications. The number of letters missed will be collected and summarized by cohort group and eye for each visit. Visual acuity data, including best corrected distance, will be presented in subject listings.

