10. CHANGES TO THE ANALYSES PLANNED IN THE PROTOCOL

This analysis plan is for an abbreviated CSR. Therefore, the primary endpoint will be summarized, but no formal statistical testing will be done. There will be no summaries for secondary endpoints. The planned summaries in the protocol for changes in corneal thickness, VA, endothelial cell count and morphology, slit lamp biomicroscopy exam findings, binocular indirect ophthalmoscopy, visual field assessment, anterior segment photos, and pupil measurement will not be created. These data will instead be available in listings.

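### The Cohorts 2/3 SAP summarises vital signs and letters missed by visit without change from baseline, although the protocol defines these safety endpoints as changes

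*SAP*

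**What the plan says.** The January 2019 SAP covers Cohorts 2 and 3. On vital signs, 9.5.1 says "Vital signs will be summarized using descriptive statistics by study visit and treatment group". On acuity, 9.5.3 says "The number of letters missed will be collected and summarized by cohort group and eye for each visit". The matching entries in the table list (14.3.3.1 and 14.3.4.1) do not mention change either.

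Elsewhere the same SAP does report change. Section 9.4 says "Continuous clinical laboratory values will be summarized using descriptive statistics for reported and change from baseline values", and 8.1 gives both the value and the change for intraocular pressure. Section 9.1 defines a general safety baseline, the last value before the implant, but 9.5.1 and 9.5.3 do not use it.

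Protocol 10.2 lists as Cohorts 2 and 3 safety endpoints "Changes in BCVA with manifest refraction using the ETDRS chart" and "Changes in body systems assessment, vital signs, and laboratory parameters". The Cohort 2 and Cohort 3 synopses introduce their lists, which include both measures, with "Safety Measures: Assessed by evaluating changes from baseline in the following".

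SAP Section 10 explains that the report is abbreviated. Among the summaries that will not be produced, with the data given in listings instead, it names "The planned summaries in the protocol for changes in corneal thickness, VA, endothelial cell count and morphology" and several other eye measures. It does not name vital signs.

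The separate Cohort 1 SAP planned a table titled "Mean and Mean Change from Baseline in Vital Sign Values by Treatment Group and Visit", a matching change table for letters missed, and a table of subjects losing three or more lines.

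**The concern.** If the endpoint is a change, a table of levels by visit leaves the reader to subtract one visit mean from another. That is sound only when the same patients stand behind both means. Here the groups have 5, 6 and 9 patients, the extensions are optional and early exit is allowed, so a different mix of patients can look like a change in patients. Even with a constant set of patients, the SD shown is the spread between patients, not the spread of change, and a large loss in one eye can be offset in the mean by small gains in others.

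Vital signs and acuity are two of the few quantitative safety tables left in the abbreviated report. Corneal thickness, endothelial counts and slit-lamp findings are reduced to listings.

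**Working it through.** The documents give no figure for this point, so the check compares schedules and then illustrates size.

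**Step 1. Who has vital signs at each late visit (protocol Tables 3 to 7)**

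| Visit | Patient exits here | Patient continues |
|---|---|---|
| Cohort 3, Month 12 (V16) | yes (Table 5) | no (Table 6) |
| Cohort 3, Month 18 (V22) | yes (Table 6) | no (Table 7) |
| Cohort 3, Month 24 (V28) | yes (Table 7) | not applicable |
| Cohort 2, Month 18 (V22) | yes (Table 3) | no (Table 4) |
| Cohort 2, Month 21 (V25) | yes (Table 4) | not applicable |

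The visit lists in protocol 13.11 to 13.15 agree with the Cohort 3 rows. In Cohort 3 the last vital signs that Table 5 schedules for everyone are at Month 6. Section 13.9 also names Month 9, which Table 5 and 13.10 do not; either way, Months 12, 18 and 24 are unaffected. The values at those three visits therefore come from non-overlapping patients. In Cohort 2 the same holds for Month 18 against Month 21, while Months 12 and 15 are measured in those who continue.

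Acuity is marked at every visit in Tables 2 to 7, for those who exit and those who continue. Its denominator changes only through early exit or a declined extension.

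**Step 2. Illustrative size when nobody changes**

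Let σ be the between-patient SD, n the group size and m the number measured at the visit. If the m are a random subset:

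SD(visit mean − group baseline mean) = σ√(1/m − 1/n)

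- n = 9 (Cohort 3 high dose, protocol 10.4), m = 3: √(1/3 − 1/9) = 0.471. For an assumed systolic σ of 10 to 20 mmHg, this is 4.7 to 9.4 mmHg.
- n = 9, m = 6: √(1/6 − 1/9) = 0.236, or 2.4 to 4.7 mmHg.
- m = n: zero.

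For two non-overlapping sets of 3, the difference in means has SD σ√(1/3 + 1/3) = 0.816σ, or 8.2 to 16.3 mmHg.

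Neither σ nor m is in the documents. They are assumptions chosen to show scale.

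**Step 3. What pairing achieves**

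With no true change, each patient's paired change is zero, so the Step 2 artefact disappears. Allow ordinary fluctuation with within-patient correlation r, for n = 9 and m = 3:

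- levels: σ√(1/3 + 1/9 − 2r/9); at r = 0.8 this is √(2.4/9) = 0.52σ
- paired change: σ√(2(1 − r)/3); at r = 0.8 this is √(0.4/3) = 0.37σ

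The two are equal at r = 0.5, and pairing is the more precise above that. It removes differences in who was measured, but not the noise of three patients.

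**Step 4. Acuity**

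One eye losing 15 letters moves the mean by 15/n: 3.0 letters (n = 5), 2.5 (n = 6) or 1.7 (n = 9). A gain of 15/(n − 1) in each other eye, that is 3.75, 3.0 or 1.9 letters, cancels it. The SAP also shows the maximum, but that does not always respond. In a simulation with normal levels and an assumed between-eye SD of 5 to 10 letters, a 15-letter loss left the group maximum unchanged in 5–35% (n = 5), 6–39% (n = 6) and 9–47% (n = 9) of cases.

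**The case against.** The report is abbreviated because the IND is being withdrawn, and Section 10 openly moves the acuity change summary to listings. With groups of 5 to 9, a reader can go through subject listings, and minimum, maximum and adverse-event tables remain. This stands: individual losses are blurred in the means but are not removed from the report. A reader might infer that the SAP conceals visual loss; the documents do not support that.

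A reader might also infer that a planned vital-sign change analysis was dropped without being declared. Protocol 18.1.2, the analysis section that Section 10 follows, does not list vital signs among its change summaries. The requirement comes from the endpoint wording in 10.2 and the synopses. The fault is a mismatch between endpoint and table, not a hidden deletion.

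Section 10 and Table 14.3.4.1 might be read as contradicting each other. They can be reconciled if Section 10 drops changes while 9.5.3 keeps levels, so this is an ambiguity.

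Nor do the documents show that attrition distorted any mean. Cohort 2 had no early discontinuations at its interim summary, and Cohort 3 Extension 1 is described for 15 patients. If all 15 reached Month 24, that mean would cover everyone.

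Finally, silence in the text might not mean levels only: the Cohort 1 SAP text on vital signs also omitted change, but its table title supplied it. Here neither text nor title does.

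**Conclusion.** The point holds in limited form. As written, the vital-sign and acuity tables do not report the endpoints that the protocol defines, although the SAP has a baseline ready and reports change for pressure and laboratory values.

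The case is strongest for Cohort 3 vital signs, where the schedule itself prevents by-visit levels at Months 12, 18 and 24 from showing change unless everyone exits at the same visit. For acuity the omission is declared and the different-patients argument does not apply; what remains is a retained table that does not measure its endpoint.

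The figure of roughly 5 to 9 mmHg rests on assumptions: 3 of 9 patients, a random subset and a systolic SD of 10 to 20 mmHg. It shrinks to zero as follow-up becomes complete. This is a worthwhile correction to descriptive tables. It does not call the conduct of the study into question.

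**What to change.** - **Table 14.3.3.1 and SAP 9.5.1:** add within-patient change from the 9.1 baseline at each visit, with the number of patients contributing.
- **Table 14.3.4.1 and SAP 9.5.3:** add within-eye change in letters missed from the same baseline, by eye and visit, with n. Add the number of eyes 15 or more letters worse than baseline. Label this as a descriptive count. Protocol 17.5 uses the three-line change only together with endothelial cell loss of at least 70%, so the count is not that serious-event criterion. One affected eye would then appear as 1 of 5, 1 of 6 or 1 of 9.
- **SAP Section 10:** reword the VA entry so that it agrees with 9.5.3 and Table 14.3.4.1.

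A row for last or worst post-dose change is optional. Pairing does not correct for selection through rescue-linked early exit, so the n at each visit should be read with the change.

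The cost is a little programming and a few lines of SAP text. No new data, visits or patients are needed.
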